## 1. INTRODUCTION

The purpose of this reporting and analysis plan (RAP) is to describe the analyses to be included in the Clinical Study Report for Protocol:

Revision Chronology of protocol 204869:		
2017N337668_00	15-OCT-2018	Original
2017N337668_01	17-JAN-2019	Amendment 1
2017N337668_02	10-SEP-2019	Amendment 2
2017N337668_03	03-SEP-2020	Amendment 3
TMF-2197350	12-NOV-2020	Amendment 4

## 2. SUMMARY OF KEY PROTOCOL INFORMATION

### 2.1. Changes to the Protocol Defined Statistical Analysis Plan

The following changes have been made to the originally planned statistical analysis specified in the 204869 protocol (amendment 4, dated 12-NOV-2020). The majority of the changes are due to GSK's decision to terminate study 204869 on 14-JAN-2021.

#### 2.1.1. Changes to Analysis Populations

The analysis populations defined in the protocol relate to the induction phase and additional analysis populations have been introduced to account for reporting in the other phases of the trial.

Per Protocol populations in Double Blind Induction and Double Blind Extended Treatment phases have been removed to simplify the reporting of efficacy.

#### 2.1.2. Changes to Interim and Final Analyses

Interim Analysis 2 (IA2), Interim Analysis 4 (IA4) and Primary Completion (PC) are documented in the protocol, but no outputs or reporting are planned due to the study team's decisions not to conduct IA2 and the termination of the study prior to IA4 and PC.

#### 2.1.3. Changes to Endpoints and Definitions

##### 2.1.3.1. Efficacy

Exploratory efficacy endpoints (excluding Serum C-Reactive Protein and Faecal Calprotectin) are documented in the protocol, but their analysis is not covered in this RAP due to the termination of the study.

##### 2.1.3.2. Biomarkers

The following biomarker endpoints are documented in the protocol, but their analysis is not covered in this RAP and may be conducted using other analysis plans:

- Proteomic profiles

- Transcriptomic profiles, including but not limited to LAG3
- Composition of immune cell populations, including but not limited to CD3+ cells by epigenetic counting or T cell receptor sequencing

The following biomarker endpoints are documented in the protocol, but their analysis is not covered in this RAP due to the termination of the study:

- 4β-hydroxycholesterol:cholesterol ratio
- Serum tryptase

Additionally, this RAP covers LAG3+ T Cells in Blood and Cell Counts in Colon reporting only in the Double Blind Induction phase because of projected lack of patients randomised to other treatment arms following study termination.

#### **2.1.3.3. Patient Reported Outcomes**

Exploratory Patient Reported Outcome (PRO) endpoints are documented in the protocol, but their analysis is not covered in this RAP due to the termination of the study.

#### **2.1.4. Changes to Efficacy Estimands and Statistical Analyses**

The “Hypothetical” additional estimand for Complete Mayo Score has been removed to simplify the reporting of efficacy.

The primary estimand (Complete Mayo Score) and key secondary estimand (Endoscopic Improvement) have been modified to account for “discontinuation due to sponsor’s decision to terminate the study” intercurrent event.

New estimands are defined for secondary continuous and categorical efficacy endpoints. The populations and intercurrent event strategies for these estimand are the same as the Primary estimand for Complete Mayo Score (in the case of secondary continuous endpoints) or Key secondary estimand for Endoscopic Improvement (in the case of secondary categorical endpoints).

The primary dose response model for Complete Mayo Score has been modified to only analyse the 450mg IV and Placebo IV arms due to projected lack of patients randomised to other treatment arms following study termination.

## 2.2. Study Objectives and Endpoints

Objectives	Endpoints
Primary 
 
• To evaluate the safety and tolerability of repeat doses of GSK2831781 during the Double-Blind Induction Phase.
 
• To characterise the efficacy dose-response of GSK2831781 during the Double-Blind Induction Phase.
 
	
 
• Incidence of adverse events and serious adverse events during the Double-Blind Induction Phase.
 
• Incidence of findings of potential clinical importance during the Double-Blind Induction Phase for: 
 
◦ Vital signs.
 
◦ Clinical laboratory values (haematology, clinical chemistry and urinalysis).
 
◦ QTc.
 
 
 
• Change from baseline in Complete 4-domain Mayo score at Week 10.
 

Secondary 
 
• To evaluate the safety and tolerability of repeat doses of GSK2831781 during the Double-Blind Extended Treatment Phase.
 
	
 
• Incidence of adverse events and serious adverse events in the Double-Blind Extended Treatment Phase.
 
• Incidence of findings of potential clinical importance during the Double-Blind Extended Treatment Phase for: 
 
◦ Vital signs.
 
◦ Clinical laboratory values (haematology, clinical chemistry and urinalysis).
 
◦ QTc.
 
 
 

 
• To investigate the effect of repeat doses of GSK2831781 on clinical efficacy including endoscopic mucosal healing during the Double-Blind Induction Phase.
 
	
 
• Adapted Mayo endoscopic score of 0 or 1 at Week 10.
 
• Adapted Mayo clinical remission at Week 10.
 
• Adapted Mayo clinical response at Week 10.
 
• Symptomatic remission over time.
 
• Change from baseline in partial Mayo score over time.
 
• Change from baseline in Adapted Mayo endoscopic score and Ulcerative Colitis
 

Objectives	Endpoints
	Endoscopic Index of Severity (UCEIS) at Week 10.

 
To investigate the effect of repeat doses of GSK2831781 on UC histologic disease activity during the Double-Blind Induction Phase.
 
	
 
Histological severity as determined by the Robarts Histopathology Index at Week 10.
 
Histological severity as determined by the Nancy Histological Index at Week 10.
 
Histological severity as determined by the Geboes Score at Week 10.
 

 
To investigate the effect of repeat doses of GSK2831781 on biomarkers of UC disease activity during the Double-Blind Induction Phase.
 
	
 
Change from baseline in serum C-reactive protein over time.
 
Change from baseline in faecal calprotectin over time.
 

 
To investigate the pharmacokinetics of GSK2831781 following subcutaneous dosing.
 
	
 
GSK2831781 PK parameters: AUC(0-tau), Cmax, tmax.
 

 
To investigate the immunogenicity of repeat doses of GSK2831781 during the Double-Blind Induction Phase.
 
	
 
Incidence of anti-drug antibodies at each visit.
 

Safety	

 
To evaluate the safety and tolerability of repeat doses of GSK2831781 in all trial phases.
 
	
 
Adverse events, vital signs, clinical laboratory values (haematology, clinical chemistry, and urinalysis), 12-lead ECG.
 

 
To investigate the immunogenicity of repeat doses of GSK2831781 in all trial phases.
 
	
 
Incidence of anti-drug antibodies at each visit.
 

Exploratory	

 
To investigate the effect of repeat doses of GSK2831781 on patient-reported outcomes in all trial phases.
 
	
 
Change from baseline in daily e-Symptom Diary, FACIT-Fatigue, Inflammatory Bowel Disease Questionnaire (IBDQ), SF-36, and PGIS.
 
PGIC at Week 10 and Week 30.
 


 
To investigate the effect of repeat doses of GSK2831781 on clinical efficacy during the Double-Blind Extended Treatment Phase.
 
	
 
Change from baseline in Adapted Mayo score between Week 10, and Week 30.
 
Adapted Mayo endoscopic score of 0 or 1 at Week 30.
 

Objectives	Endpoints
	
 
Adapted Mayo clinical remission at Week 30.
 
Adapted Mayo clinical response at Week 30.
 
Change from baseline in Adapted Mayo endoscopic score and Ulcerative Colitis Endoscopic Index of Severity (UCEIS) at Week 30.
 
Symptomatic remission over time.
 
Change from baseline in Partial Mayo score over time.
 
Change from baseline in histological severity as determined by the Robarts Histopathology Index, Nancy Histological Index and Geboes Score at Week 30.
 
Clinical response at Week 10, maintained at Week 30.
 
Clinical remission at Week 10, maintained at Week 30.
 

 
To investigate the effect of repeat doses of GSK2831781 on oral corticosteroid use for participants using corticosteroids at baseline.
 
	
 
Corticosteroid-free Adapted Mayo clinical remission at Week 30 (with at least 28 consecutive days corticosteroid-free, including Weeks 26 to 30).
 
Change from baseline daily corticosteroid dose to average daily corticosteroid dose during the taper period.
 

 
To investigate the effect of repeat doses of GSK2831781 on biomarkers of disease activity in patients moderate to severe active UC during the Double-Blind Extended Treatment Phase and Open Label Treatment Phases.
 
	
 
Change from baseline in serum C-reactive protein over time.
 
Change from baseline in faecal calprotectin over time.
 


 
To investigate the effect of repeat doses of GSK2831781 on colon biopsy tissue and blood biomarkers in patients with moderate to severe active UC in all Treatment Phases.
 
	
 
Change from baseline in colon biopsy tissue biomarkers at Week 10 and Week 30, which may include but not be limited to: 
 
Number of LAG3+ and CD3+ cells by IHC.
 
 
 

Objectives	Endpoints
	
 
○ Composition of immune cell populations, including but not limited to CD3+ cells by epigenetic counting or T cell receptor sequencing.
 
○ Transcriptomic profiles, including but not limited to LAG3.
 
● Change from baseline in blood biomarkers, which may include but not be limited to: 
 
○ Number of LAG3+ cells at Week 10 and Week 30.
 
○ 4β-hydroxycholesterol:cholesterol ratio.
 
○ Serum tryptase.
 
○ Proteomic profiles.
 
 
 

 
● To investigate the effect of repeat doses of GSK2831781 on plasma sLAG3 in patients with moderate to severe active UC in all Treatment Phases.
 
	
 
● Soluble LAG3 (sLAG3) concentrations.
 

 
● To evaluate the concentration-time profiles of GSK2831781 after repeat intravenous and subcutaneous dosing in all Treatment Phases.
 
	
 
● GSK2831781 PK concentrations.
 

	
 
● Change from baseline in Adapted Mayo score between Week 10, and Week 22.
 
● Adapted Mayo endoscopic score of 0 or 1 at Week 22.
 
● Adapted Mayo clinical remission at Week 22.
 
● Adapted Mayo clinical response at Week 22.
 
● Change from baseline in Adapted Mayo endoscopic score and Ulcerative Colitis Endoscopic Index of Severity (UCEIS) at Week 22.
 
● Change from baseline in histological severity as determined by the Robarts
 

Objectives	Endpoints
	
Histopathology Index, Nancy Histological Index and Geboes Score at Week 22.
 
 
• Clinical response based on partial Mayo score at Week 22, maintained at Week 42.
 
• Clinical remission based on partial Mayo score at Week 22, maintained at Week 42.
 
• Symptomatic remission over time.
 
• Change from baseline in partial Mayo score over time.
 

 
• To investigate the effect of repeat doses of GSK2831781 on extraintestinal manifestations in all Treatment Phases.
 
	
 
• Incidence of extraintestinal manifestations over time.
 

**Footnotes:**

[figure not shown]
- 1 Potential clinical importance is defined in Section 15.8 for each relevant safety endpoint.
- 2 The Complete 4-domain Mayo score is used for the primary endpoint due to its wider dynamic range for assessment of dose-response compared to the Adapted Mayo score used for secondary and exploratory endpoints.
- 3 Clinical response and remission for the various iterations of Mayo score are defined in [Appendix 7](#), Section 15.7.
- 4 Symptomatic remission is defined as a rectal bleeding subscore of 0, and a stool frequency subscore of  $\leq 1$ , with no worsening from baseline.
- 5 Taper period is defined from the start of the taper (Weeks 12 or 24, respectively, for the Double-Blind and Open Label Extended Treatment Phases) to completion of the respective Extended Treatment Phases.

## 2.3. Study Design

[figure not shown]
Overview of Study Design and Key Features				
Screening Up to 35 days	Induction Phase (IP) 10 weeks	Extended Treatment Phase (ETP) 20 weeks	Follow-Up	
Week -5	0	10	30	42 54

★ = Endoscopy and biopsy
				
Design Features	
 
Phase 2, multicentre, randomized, double-blind parallel, placebo-controlled
 
Double-blind Induction Phase up to 10 Weeks for all participants
 
At Week 10, all participants undergo an Induction Assessment, including centrally read endoscopy. Responder status is identified by the results of the assessment of clinical response calculated by the eCRF and determines the participant's subsequent path through the study.
 
 
Week 10 Responders
 
 
Participants identified as Responders who received GSK2831781 during the Induction phase will then receive 300mg GSK2831781 subcutaneously (SC) every four weeks during the double-blind Extended Treatment Phase (ETP), from Week 14 until Week 26.
 
Week 10 Responders in the placebo group during the Induction phase will continue to receive placebo SC every four weeks in the double-blind ETP.
 
At Week 30, all participants in the Responder ETP will undergo an Assessment, including a centrally read endoscopy. Subsequently, all participants will remain in study, but off treatment, to Week 42 in the 12-week Follow-Up phase.
 
			

## Overview of Study Design and Key Features

## Extended Treatment Phase – Dosing regimen for Responders only

## Open Label Treatment – Dosing Regimen for Non-Responders

## Week 10 Non-Responders

- Participants identified as Non-Responders at Week 10 will be assigned to open label treatment in the Open Label Induction Phase. The total duration of open label treatment will be up to an additional 30 weeks of treatment (Week 12 to Week 42) and a 12-week Follow-Up. Participants who have not attained clinical response, determined following a centrally read endoscopy at Week 22 (calculated centrally through the eCRF), will discontinue study treatment and are still required to attend a Follow-Up visit approximately 16 weeks from the last dose event.
- Participants in the Open Label part who respond at Week 22 will then receive 300mg GSK2831781 subcutaneously (SC) every four weeks during the Open Label Extended Treatment Phase (ETP), from Week 26 until Week 38.
- Subsequently, all Open Label participants will remain in study, but off treatment, to Week 54 in the 12-week Open Label Follow-Up phase.

[figure not shown]
Overview of Study Design and Key Features	
Dosing	
INDUCTION Phase:
 
 
• GSK2831781 450 mg IV
 
• GSK2831781 300 mg IV
 
• GSK2831781 150mg IV
 
• GSK2831781 45mg IV
 
• Placebo IV
 
 
EXTENDED Treatment Phase for RESPONDERS
 
 
• GSK2831781 300 mg SC
 
• Placebo SC
 
 
OPEN LABEL Treatment Phase for NON-RESPONDERS
 
 
• GSK2831781 450 mg IV – weeks 12, 14, 18 and 22
 
• GSK2831781 300 mg SC for Open Label Responders (assessed at week 22)
 
• Treatment discontinuation for Open Label Non-Responders (assessed at week 22)
 

Time & Events	
 
• Refer to Appendix 2: Schedule of Activities (SoA)
 

Treatment Assignment	
 
• At Screening a unique Participant Number (case report form (CRF) number) will be assigned to any participant who has at least one Screening procedure performed, other than informed consent. The unique Participant Number will be used to identify individual participants during the study.
 
• Participants who meet the screening eligibility criteria will be randomised to a treatment group through RAMOS NG. RAMOS NG will confirm the participants CRF number (Participant number) and provide the randomisation number. The randomization is centrally controlled by RAMOS NG. Once the randomization number is assigned, it cannot be reassigned to another participant in the study.
 
• At the start of the study, participants will be randomised in a 2:1 ratio to GSK2831781 450mg and Placebo.
 
• When an appropriate number of participants have been randomised in these two arms for the interim analysis (Interim Analysis 3, see below), randomisation to all dose regimens (GSK2831781 450mg, 300mg 150mg, 45mg or placebo) will be opened in the ratio 2:3:3:3:2.
 
• The randomisation will be stratified according to: 
 
1. Country (Japan or not Japan); if not Japan further stratification by:
 
2. Prior advanced therapy experience (advanced therapy naïve, experienced a single class of advanced therapy, or experienced multiple classes of advanced therapies).
 
 
 
• There is no re-randomisation for the ETP – if the participant is a placebo responder then the participant will stay on blinded placebo
 
• At least 242 evaluable participants who complete all Week 10 assessments or withdraw will be recruited. The study size will not exceed 320 participants.
 

Interim Analysis	
Up to 4 interim analysis will be conducted to assess the safety, pharmacokinetics, pharmacodynamics and efficacy of GSK2831781. Recruitment will continue while the interim analyses are being conducted, except in the case of a safety concern.
 
 
• Interim Analysis 1 – PK
 
• Interim Analysis 2 – Early Efficacy
 
• Interim Analysis 3 – Efficacy futility
 

Overview of Study Design and Key Features	
	

• Interim Analysis 4 – Pharmacodynamic Blinded safety data, including clinical laboratory parameters and adverse events will be reviewed at appropriate intervals during the study conduct by an internal GSK SRT team according to routine pharmacovigilance practice. At the interim analyses, the data will be reviewed by the Data Review Committee (DRC) to ensure objective medical and statistical review of safety and efficacy issues to protect the ethical and safety interests of participants and to protect the scientific validity of the study via review of unblinded study data.

[Figure 1](#) below shows the paths that a participant can take through the study. White rectangles are double blinded phases, grey rectangles are unblinded (open label or off drug phases). Note that at any point participants can discontinue from study drug but continue in the study until the end of the study phase.

- Group A: Induction Phase
- Group B: Extended Treatment Phase (Week 10 Responders)
- Group C: Open Label Induction (Week 10 Non-Responders)
- Group D: Open Label ETP (Week 22 Responders)
- Week 22 Non-responders will complete a follow-up visit and withdraw from the study.

The strategy for reporting study phases is to use analysis populations to define the participants for each phase. Post-Week 22 data for Week 22 Non-responders will be listed, not summarised.

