6.4. Measures to Minimize Bias: Randomization and Blinding

6.4.1. Method of Treatment Assignment

At Screening a unique Participant Number (case report form (CRF) number) will be assigned to any participant who has at least one Screening procedure performed, other than informed consent. The unique Participant Number will be used to identify individual participants during the study.

Participants who meet the screening eligibility criteria will be randomised to a treatment group through RAMOS NG. RAMOS NG will confirm the participant's CRF number (Participant number) and provide the randomisation number, where a randomisation number will be assigned from a randomisation schedule generated by Clinical Statistics, prior to the start of the study, using validated internal software. Once assigned, this number must not be reassigned to any other participant in the study.

Therefore, the randomisation is centrally controlled by RAMOS NG.

Randomisation of participants must be undertaken prior to dosing, preferably on Day 1, but may be conducted on Day -1 if required to allow the site pharmacist to prepare the dose. Randomisation may only occur if all information pertaining to patient eligibility has been confirmed, including eCRF Mayo score eligibility calculation.

The total number of participants recruited to the study will be up to a maximum of 320. At the start of the study, participants will be randomised in a 2:1 ratio to GSK2831781 450 mg and Placebo. When an appropriate number of participants have been randomised in these two arms for the interim analysis (Interim Analysis 3, see Section 9.5), randomisation to all dose regimens (GSK2831781 450 mg, 300 mg 150 mg, 45 mg or Placebo) will be opened in the ratio 2:3:3:2.

Randomisation will first be stratified by ethnicity (Japanese or non-Japanese participant). For the purposes of stratification, a Japanese participant must be living in Japan at the time of randomisation. Non-Japanese participants will be further stratified according to prior treatment (advanced therapy naïve, experienced a single class of advanced therapy, or experienced multiple classes of advanced therapies).

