To ensure balance across the doses within Japanese participants, recruitment to GSK2831781 450 mg or placebo in a 2:1 ratio may continue after all dose regimens have been opened. When an appropriate number of Japanese participants have been dosed to GSK2831781 450 mg or placebo in a 2:1 ratio, recruitment to the remaining doses will continue using the same ratio as the rest of the participants. Due to number of expected Japanese participants, randomisation within this group will not be stratified according to prior treatment.

The treatment codes are as follows:

Treatment Code	Treatment Description
A	GSK2831781 450 mg
B	GSK2831781 300 mg
C	GSK2831781 150 mg
D	GSK2831781 45 mg
P	Placebo

Following the double-blind Induction Phase of the study, participants will be allocated to the next treatment phase according to their Responder status:

Responder status at Week 10	Treatment Phase
GSK2831781 Responder	Double-blind Extended Treatment Phase 
 • GSK2831781 300 mg SC every four weeks
Placebo Responder	Double-blind Extended Treatment Phase 
 • Placebo SC every four weeks
Non-Responder	Initiate Open Label Induction Phase followed by Open Label Extended Treatment Phase

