### 8.1.1.2. Statistical Analysis

Bayesian analysis for continuous endpoint	
Endpoints	Change from baseline in Complete Mayo Score at Week 10
Statistical analysis	Linear regression
Predictors	
 
● TRT = study treatment(categorical)
 
● Advanced Therapy Experience (categorical) (includes interaction with study treatment)
 
● Baseline Complete Mayo (continuous)
 
● Duration of disease, years (continuous)
 

Model	$y_i \sim \text{Normal}(\text{mean}=\mu, \text{SD}=\sigma)$ $\mu = (\text{TRT=Placebo}) \times (\text{Experienced}=Y) \times \beta_1 +$ $(\text{TRT}=450\text{mg}) \times (\text{Experienced}=Y) \times \beta_2 +$ $(\text{TRT=Placebo}) \times (\text{Naive}=Y) \times \beta_3 + (\text{TRT}=450\text{mg}) \times (\text{Naive}=Y) \times \beta_4$ $+ (\text{Duration}^*) \times \beta_5 + (\text{Baseline}^*) \times \beta_6$

Bayesian analysis for continuous endpoint	
Population-level coefficients ( $\beta$ )	
 
• <math>\beta</math> = fixed effects, parameters associated to predictors  <math>\beta_k</math>: non-informative prior distributions,  <math>\beta_k \sim \text{Normal}(\text{mean}=0, \text{SD}=100)</math>
 
• Standard deviation <math>\sigma</math>:  Non-informative prior Gamma distribution (shape=2, rate=0.1) (Chung, 2013)
 

\* Unless otherwise specified the predictors (not including study treatment) will be centred around their estimated mean in the model

Further details of primary analysis	
Model diagnostics and checking	
	
 
• Each chain will initially have length Of 1,000,000, thin of 10 and burn-in length of 50,000.
 
• Chain convergence diagnostics will be saved in HARP (refdata folder) and inspected.
 
• The MCSE will be compared with the standard deviation of the posterior distribution (SD) to ensure that only a fraction of the posterior variability is due to simulation error, i.e., the ratio MCSE/SD should be close to 0.01
 

Model results presentation	

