### 8.1.1.3. Additional analyses for the Primary Endpoint

Frequentist analysis of change from baseline in Complete Mayo score at Week 10	
	
A fixed-effect normal linear model will be used to compare the primary endpoint (change from baseline in Complete Mayo score at Week 10 Double-Blind Induction) between 450mg GSK2831781 IV and Placebo IV.
 
The following variables will be used as covariates: Duration of disease (continuous), Advanced Therapy Experience (Categorical), Baseline Complete Mayo (continuous) and treatment.
 
The estimated difference in change from baseline in Complete Mayo score at Week 10 will be displayed with 95% confidence interval (and associated p-value).

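### Japan v not Japan is the first randomisation stratum and may keep its own 450 mg:placebo ratio, yet no efficacy model adjusts for it; the likely effect is small, and the linear models can be corrected cheaply.

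*SAP*

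**What the plan says.** **Stratification.** SAP 2.3 (Treatment Assignment) lists the first stratum as "Country (Japan or not Japan); if not Japan further stratification by" prior advanced therapy. Protocol 6.4.1 says "Randomisation will first be stratified by ethnicity (Japanese or non-Japanese participant") and requires that a Japanese participant be living in Japan. Japanese participants are not further stratified by prior therapy, because few are expected.

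**Allocation.** According to the SAP, "At the start of the study, participants will be randomised in a 2:1 ratio to GSK2831781 450mg and Placebo"; later all arms "will be opened in the ratio 2:3:3:3:2", which is 1:1 for 450 mg v placebo. (Protocol 6.4.1 prints only four figures for the five arms; the ratio used here is the SAP's.) For Japan, Protocol 6.4.1 adds that "recruitment to GSK2831781 450 mg or placebo in a 2:1 ratio may continue after all dose regimens have been opened". Once enough Japanese participants have been dosed, "recruitment to the remaining doses will continue using the same ratio as the rest of the participants".

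**Models.** The primary Bayesian model (SAP 8.1.1.2) has treatment, baseline, disease duration and "Advanced Therapy Experience (categorical) (includes interaction with study treatment"). For the frequentist model (8.1.1.3), "The following variables will be used as covariates: Duration of disease (continuous), Advanced Therapy Experience (Categorical), Baseline Complete Mayo (continuous) and treatment". The logistic model (8.2.1.2, reused for clinical remission in 8.2.2) and the repeated-measures model (8.2.3.1) have no country term either. Country is not in the covariate list in SAP 5.4.1, and 5.3 plans no adjustment for centre. SAP 5.4.1 leaves room for further strata but names none.

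**The concern.** The probability of receiving 450 mg rather than placebo can depend on country within the same calendar period, and country is then left out of the analysis. Since termination, 450 mg v placebo is the whole of the primary efficacy comparison (SAP 2.1.4 and 2.4), and it is exactly this pair whose ratio may differ.

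Two things follow if country predicts outcome:

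- In a linear model, the between-country variation stays in the residual and the standard error is larger than it need be.
- If the final 450 mg:placebo ratio also differs by country, part of the country difference passes into the treatment estimate.

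The term for advanced therapy experience does not stand in for country, because Japan is not stratified by it. The models do adjust for disease duration, which is not a stratification factor, and no reason is given for leaving out the first one.

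**Working it through.** **1. The plan's own figures.** Stage 1 is 40:20 (Protocol 9.2.1, Interim Analysis 3). The remaining 242 − 60 = 182 at 2:3:3:3:2 gives units of 182/13 = 14, so 28/42/42/42/28. Totals are 40 + 28 = 68 on 450 mg, 42 on each lower dose and 20 + 28 = 48 on placebo. This matches Protocol 9.2.1 exactly. The overall 450 mg:placebo ratio is 68/48 = 1.42, against 2 for a Japanese stratum kept in stage 1, so ratios that differ by country are possible.

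**2. Inputs.** From Protocol 9.2.1: SD 1.5. Assumed, because not given: 12 to 48 Japanese participants across the two arms, and a country effect d of 0.5 to 1.5 Mayo points. In the terminated-trial rows, the non-Japanese split of 44:24 is also assumed.

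**3. Formulas.** Let p be the Japanese share of an arm of size n.

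- Bias = (p on 450 mg − p on placebo) × d.
- SE² without the country term = sum over the two arms of [2.25 + d²p(1−p)]/n.
- SE² with the term = 2.25 / Σw, where w = n₄₅₀·n_pbo/(n₄₅₀ + n_pbo) within each country stratum.

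Worked case, planned size with Japan 16:8 and the rest 52:40, d = 1:

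- Shares are 16/68 = 0.235 and 8/48 = 0.167, so bias = 0.069.
- SE without the term = √[(2.25 + 0.180)/68 + (2.25 + 0.139)/48] = 0.292.
- Σw = 5.33 + 22.61 = 27.94, so SE with the term = 1.5/√27.94 = 0.284. The ratio is 1.03.

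| Case (450 mg:placebo) | Share difference | Bias, d = 0.5 to 1.5 | SE excess without term |
|---|---|---|---|
| Planned: Japan 8:4, rest 60:44 | 0.034 | 0.02–0.05 | 0.3–4% |
| Planned: Japan 16:8, rest 52:40 | 0.069 | 0.03–0.10 | 0.5–7% |
| Planned: Japan 32:16, rest 36:32 | 0.137 | 0.07–0.21 | 0.3–10% |
| Planned: Japan 17:12, rest 51:36 | 0 | 0 | 1–9% |
| Terminated: Japan 8:4, rest 44:24 | 0.011 | 0.005–0.016 | 0.7–6% |
| Terminated: Japan 16:8, rest 44:24 | 0.017 | 0.008–0.025 | 1–9% |
| Stage 1 only: Japan 8:4, rest 40:20 | 0 | 0 | 0.8–7% |

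**4. A second set of terminated-trial numbers.** Assume 3 to 9 participants per middle dose, so 2:2 to 6:6 more on 450 mg and placebo, and 12 to 36 Japanese all at 2:1.

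- Low end: 8/50 − 4/26 = 0.006.
- High end: 24/70 − 12/38 = 0.027.

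That is 0.006 to 0.027 points per 1-point country effect, against an SE of 0.30 to 0.36. At d = 1.5 the high corner reaches 0.027 × 1.5 = 0.04.

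**5. Logistic models.** Simulation of 1,500 trials per case used placebo 20% (Protocol 9.2.1), 450 mg about 40% (assumed), country log odds ratio 0.7 or 1.4 (assumed), and maximum-likelihood fits without the SAP's priors.

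- Adding country raises the SE of the log odds ratio: 0.434 to 0.441 (Japan 16:8, 0.7) and 0.411 to 0.439 (Japan 17:12, 1.4).
- The SD of the risk difference hardly moves in those two cases: 0.0837 to 0.0845, and 0.0841 to 0.0841.
- With Japan at 16:8 in the planned trial, the unadjusted risk difference is 0.220 (log odds ratio 0.7) or 0.232 (1.4), against 0.210 adjusted.

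**6. Sparse stratum.** With 12 Japanese participants, the chance of no responders is 0.8¹² = 7% at a 20% rate and 0.9¹² = 28% at an assumed 10%. Illustrative data (assumed): non-Japan 16/43 v 5/23, Japan 0/8 v 0/4. The fit uses the SAP 8.2.1.2 priors with Prior 2 from 15.14.1 and no other covariates. Adding a centred country term with a Normal(0, SD=100) prior drops the median risk difference from 0.14 to about 0.06.

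**The case against.** The strongest reply is that the effect is small in the trial that this SAP analyses. The SAP was rewritten after termination, and 2.4 reports few participants in the middle doses. In stage 2 each middle dose receives three participants for every two on 450 mg and two on placebo, so few middle-dose participants means few 1:1 allocations, and the non-Japanese also end near 2:1. Protocol 6.4.1 says only that the separate ratio may continue, and then returns Japan to the common ratio; if Japan ends in the same mix as the rest, bias is zero. A 1-point country effect equals the whole assumed placebo change of −1, and would have to survive adjustment for baseline, duration and therapy experience. All of this stands. It limits the size, but it does not explain the omission.

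A second reply is that SAP 5.4.1 allows further strata to be considered. That does not supply the adjustment: it names none, and it leaves the choice open.

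A third is that a vague country term can harm the logistic models when the Japanese stratum is sparse. That also stands. The placebo coefficient carries the informative prior and covariates are centred, so a country coefficient that drifts far from zero pulls down both arm rates.

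A reader might infer that the intervals are too wide throughout. The documents do not support that: it holds only in the linear models, and only if country is prognostic. In the logistic models the term gave no precision gain. Nor do the documents show that country actually confounds the comparison; that needs both a country effect and unequal final ratios, and neither is reported.

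**Conclusion.** The omission is real: the first randomisation stratum, with a ratio that may differ from the rest, appears in no efficacy model and is not in the covariate list. Its consequence is modest and conditional.

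- **Precision, linear models:** if country is prognostic, standard errors are about 0.3% to 10% too wide, for assumed effects of 0.5 to 1.5 points. The error is on the conservative side.
- **Bias:** if the final ratio also differs by country, about 0.005 to 0.03 Mayo points under the assumed terminated-trial numbers (0.04 in the extreme corner of step 4). At planned size it is up to about 0.2 in the most extreme case, with 48 Japanese participants all at 2:1 and a 1.5-point effect. The plan calls a 2-point difference clinically meaningful.
- **Logistic models:** no precision gain from adjusting, so any case for the term there rests on bias alone: 1 to 2 percentage points in the planned-size simulation with Japan at 2:1.

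The number of Japanese participants, the country effect and the final ratio by country are all assumptions. Nothing here shows that a conclusion would change.

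**What to change.** - Add a Japan/not-Japan main effect to the linear models in SAP 8.1.1.2, 8.1.1.3 and 8.2.3.1. In the two Bayesian models give it the Normal(0, SD=100) prior already used for the other coefficients.
- List the factor in SAP 5.4.1, and show each linear model without it as a sensitivity analysis.
- Tabulate treatment arm by Japan/not Japan, so that the final ratios can be seen.
- In the logistic models (SAP 8.2.1.2 and its reuse in 8.2.2) leave the main analysis as it is. Add country only as a sensitivity analysis, with a weakly informative prior, because a vague prior on a sparse stratum can distort the arm response rates.

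The cost is one extra parameter per model, one table and some SAP wording. The factor is already recorded for randomisation.
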